4.6.2 Childhood Developmental Milestones

The infant's developmental milestones will be assessed using the Ages and Stages Questionnaire version 3 (ASQ-3), in the domains of communication, gross motor, fine motor, problem solving, and personal-social at months 2, 4, 6, 9, and 12.

The total score for each domain will be summarized by visit using summary statistics in the SAFI.

In addition, the number and percentage of infants with abnormal scores (Yes/No) will be presented in the SAFI, as per cut-offs below transcribed from the ASQ-3 User's guide:

ASQ-3	Area				
questionnaire	Communication	Gross Motor	Fine Motor	Problem Solving	Personal- Social
Month 2	22.77	41.84	30.16	24.62	33.71
Month 4	34.60	38.41	29.62	34.98	33.16
Month 6	29.65	22.25	25.14	27.72	25.34
Month 9	13.97	17.82	31.32	28.72	18.91
Month 12	15.64	21.49	34.50	27.32	21.73

ASQ-3 = Ages and Stages Questionnaire version 3.

Values below the respective cut-off will be classified as abnormal (i.e., further assessment with a professional may be needed).

A corresponding listing will be produced.

Only questionnaires assigned to the correct time point will be included in the main analysis. If the wrong questionnaire is used for some time points in >20% infants, a sensitivity analysis will be performed with these data included.

4.6.3 Women's Disease Activity

To assess disease activity in women the EDSS score, a neurological examination and potential relapses are collected at baseline, early discontinuation and unscheduled visits if applicable. This will be summarized as follows in the FASM:

Relapse:

- Number of relapses before/during pregnancy (defined by LMP) and after pregnancy (defined as after birth) will be summarized in 3-month intervals
- Number and percentage of women in each category $(0, 1, 2, 3 \text{ and } \ge 4)$ in 3-month intervals of before/during/after pregnancy
- Among women who received their last ocrelizumab within 12 months before the LMP:
 - Number of relapses between 6-9 months after last ocrelizumab dose before Baseline
 - Number of relapses in the 3 months after the first post-partum ocrelizumab dose.
- Annualized relapse rate and 95% CI may also be presented in 3-month intervals if warranted by the number of data points

- Presence of any clinically significant abnormalities from the neurological examination (Yes, No)
- Type of neurological abnormality (disability progression independent of relapse, MS relapse, signs or symptoms suggestive of Progressive Multifocal Leukoencephalopathy, Other)

Corresponding listings will be produced for relapses, EDSS, neurological examination findings.

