#### 1.3 STUDY RATIONALE AND BENEFIT-RISK ASSESSMENT

Most patients with MS are women in their reproductive years (Albor et al. 2017; Trojano et al. 2012). The appropriate treatment strategy during pregnancy and after birth remains uncertain, since none of the many DMTs available for MS are recommended during pregnancy or breastfeeding (LaHue et al. 2019). There is no consensus on how soon after birth may DMTs be safely resumed. Women often have to choose between breastfeeding and early resumption of a disease-modifying therapy (DMT) postpartum. This can have a significant impact on disease management since the risk of postpartum relapse is high. About 30% of women experience a relapse in the first 3 months postpartum (Vukusic et al. 2004). Such relapses may in turn worsen disability (Portaccio et al. 2014).

The general benefits of breastfeeding are well established, both for mothers as well as for infants. Infants who are exclusively breastfed have a lower risk of gastrointestinal as well as respiratory infections (Kramer and Kakuma 2012), and mothers who breastfeed have a reduced risk of breast, ovarian, and endometrial cancer (Ip et al. 2007; Kramer and Kakuma 2012; Jordan et al. 2017; Collaborative Group on Hormonal Factors in Breast Cancer, 2002). In addition, there is good evidence that exclusive breastfeeding may reduce the risk of postpartum relapses. A systematic literature review/meta-analysis of 24 studies exploring the association between breastfeeding and MS relapse reported a pooled adjusted hazard ratio (HR) for the association of breastfeeding and postpartum relapses of 0.57 (95% CI: 0.38 to 0.85; p=0.006) vs. non-breastfeeding (Krysko et al. 2020); and a study of a cohort of 466 pregnancies in

375 women with MS (based on electronic health records) found that exclusive breastfeeding reduced the risk of early postpartum relapses (adjusted HR=0.37, p=0.009; Langer-Gould et al. 2020). Despite reduction in postpartum relapses with breastfeeding, annual relapse rates remain fairly high after birth, highlighting the need for additional strategies to prevent such relapses (Krysko et al. 2020). An efficacious mAb therapy that could safely be resumed soon after birth would significantly reduce the risk of postpartum relapses (LaHue et al. 2020).

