ADID = average oral daily infant dosage; ASQ-3 = Ages and Stages Questionnaire, version 3; AUC = area under the milk concentration-time curve; CIS = clinically isolated syndrome; EDSS = Expanded Disability Status Scale; HBV = hepatitis B virus; Hib = Hemophilus influenzae type b; LLN = lower limit of normal; LMP = last menstrual period; MDID = maximum oral daily infant dosage; MMR = measles, mumps, and rubella MS = multiple sclerosis; PCV-13 = 13-pneumococcal conjugate vaccine; RID = relative infant dose; WHO = World Health Organization.

Table 1 Objectives and Corresponding Endpoints (cont.)

Objectives	Corresponding Endpoints	
Exploratory Objectives		
To evaluate infant's growth velocity and developmental milestones in the first year of life	Assessment of growth velocity based on age- adjusted length, weight, head circumference, using monthly growth charts according to the WHO Child Growth Standards, as well as absolute values at Months 2, 4, 6, 9, and 12	
	
 
Assessment of child developmental milestones in the domains of communication, gross motor, fine motor, problem solving, and personal-social at Months 2, 4, 6, 9, and 12, using the ASQ-3
 
	
To measure disease activity in lactating women with CIS or MS receiving ocrelizumab postpartum	Number of MS relapses during the postpartum period (clinical relapses)	
	Mean change in the EDSS score from last pre-baseline measurement (up to 1 year before LMP) to baseline	
To evaluate the evolution of B-cell levels over the first year of life in infants of lactating women with CIS or MS receiving ocrelizumab postpartum	Trajectory (absolute and percentage changes) of B-cells (CD19 + cells) in the infant from Day 30 after the mother's first ocrelizumab postpartum infusion to 1 month after the first or second dose of MMR vaccine, or Month 13 of age in case MMR vaccine is not planned to be administered	

ADID=average oral daily infant dosage; ASQ-3=Ages and Stages Questionnaire, version 3; AUC=area under the milk concentration-time curve; CIS=clinically isolated syndrome; EDSS=Expanded Disability Status Scale; HBV=hepatitis B virus; Hib=Hemophilus influenzae type b; LLN=lower limit of normal; LMP=last menstrual period; MDID=maximum oral daily infant dosage; MMR=measles, mumps, and rubella MS=multiple sclerosis; PCV-13=13-pneumococcal conjugate vaccine; RID=relative infant dose; WHO=World Health Organization.

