# 3.1.3 Treatment and Sampling Period

Women fulfilling the inclusion/exclusion criteria will receive the ocrelizumab dose regimen as per the locally approved label. The first dose of ocrelizumab may be administered at any point between Week 2 and Week 24 postpartum, as an initial split dose of two 300 mg infusions (in 250 mL 0.9% sodium chloride) separated by 14 days or as a single 600 mg infusion (in 500 mL 0.9% sodium chloride), according to the local prescribing information. For women where a decision not to administer a second 300 mg infusion is taken after enrolment, continuation in the study will be allowed. Dosing and treatment duration are at the discretion of the physicians, in accordance with local clinical practice and local labeling (U.S. Prescribing Information [USPI]; Summary of Product Characteristics [SmPC]). If women did not experience a serious infusion-related reaction (IRR) with any previous ocrelizumab infusion, a shorter (2-hour) infusion can be administered for subsequent 600 mg doses (SmPC, USP). Women referred by healthcare professionals (HCPs) to participate in the trial may receive ocrelizumab treatment at their neurologist's site as part of their standard of care treatment.

Maternal breastmilk samples will be collected over several time points up to  $60~(\pm 2)$  days after the first postpartum ocrelizumab infusion at approximately the same time of day, although flexibility is allowed on collection timings to accommodate the mother and infant feeding schedule. The only exception is the first (Day 1) post-infusion breastmilk sample, and in women who received a  $2\times300~\text{mg}$  dose, the second (Day 15) post-infusion breastmilk sample, which should be collected 24 hours after the midpoint of the infusion. On days of collection, milk should be expressed from both breasts until completely emptied using an electric breast pump. The milk from each breast is then mixed and a sample (volume = 5~mL) is removed for analysis. The infant can be bottle-fed the remaining expressed milk. If the infant is not usually fed using a bottle, milk may be expressed from one breast only. If the mother presents with unilateral

mastitis, milk should only be expressed from the unaffected breast, until the infection resolves. If mastitis presents bilaterally (rare), breastmilk collection should be stopped until the infection resolves.

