To further understand the extent of ocrelizumab transfer through breastmilk and the exposure in infants, secondary endpoints will include the area under the milk concentration-time curve (AUC) of ocrelizumab in breastmilk over 60 days post-ocrelizumab infusion, average concentration, peak concentration, time to peak

concentration and the maximum (oral) daily infant dosage (MDID), as recommended by the FDA (FDA 2019). To evaluate potential adverse impact on the infants, infant health and development outcomes will be assessed using growth charts according to the WHO Child Growth Standards (WHO 2022) and the ASQ-3, a widely accepted tool for measuring development in young children (Lipkin et al. 2020; American Association of Pediatrics Policy Statement 2006).

A Phase IIIb study examining the effect of ocrelizumab treatment on the humoral responses in RMS patients found that patients who received ocrelizumab and were peripherally B-cell depleted were nevertheless able to mount humoral responses (though attenuated) to clinically relevant vaccines (tetanus toxoid, 23-valent pneumococcal polysaccharide vaccine and influenza; Bar-Or et al. 2020). Vaccine-induced antibody titers will similarly be measured in this study to check whether infants of lactating women with CIS or MS receiving ocrelizumab postpartum can mount a protective immune response to clinically relevant vaccines.

As exploratory endpoints, disease activity will be measured in the mothers using standard assessments such as Expanded Disability Status Scale (EDSS) and number of MS relapses. These endpoints are commonly used in MS clinical trials to assess treatment efficacy and disease progression.

As recommended (FDA 2019), this study is designed to minimize burden on the mother and disruption to the infant's feeding schedule. For example, at sample collection time (when the infant would be fed the remainder of the collected milk through a bottle), mothers may instead collect the sample from only one breast if the infant is not normally fed using a bottle. Further, the infant blood sample on Day 30 ( $\pm 2$  days) post-infusion and at 1 month ( $\pm 30$  days) after the first or second dose of MMR vaccine/Month 13 of age ( $\pm 30$  days) may be collected at home by a visiting nurse, or at the hospital as part of study visits.

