### 4.1.1 Inclusion Criteria

The following criteria must be met for study entry:

- An Informed Consent Form (ICF) for participation of the maternal subject and her infant (for collection of blood, infant demographic and adverse event data) is signed and dated by the subject. Where applicable, the written ICF with respect to the infant is also signed and dated by the holder of parental rights as designated by the maternal subject
- Woman is able and willing to comply with the study protocol, according to the judgment of the investigator, in particular:
  - Woman is willing to breastfeed (either exclusively, or with formula supplementation) for at least 60 days after the first postpartum ocrelizumab infusion (this decision is to be taken prior to and independent from study participation)
  - Woman is willing to provide breastmilk samples before and after their first and, if applicable, second postpartum ocrelizumab infusion
    - Note: Exposure to ocrelizumab includes administration of an initial split dose of two 300 mg infusions (in 250 mL 0.9% sodium chloride) separated by 14 days for women initiating treatment with ocrelizumab, or a single 600 mg infusion (in 500 mL 0.9% sodium chloride) for women already on treatment with ocrelizumab.
- Woman is between 18 and 40 years of age at screening
- Woman has a diagnosis of MS or CIS (in line with the locally approved indications)

- Woman has delivered a healthy term singleton infant (≥37 weeks gestation)
- Infant is between 2–24 weeks of age at the time of the mother's first postpartum dose of ocrelizumab
- For women who received commercial ocrelizumab (OCREVUS) before enrolment: documentation that last exposure ocrelizumab occurred more than 3 months before the LMP (i.e., excluded a potential fetal exposure) and was given at the approved dose of 2×300 mg or 1×600 mg
- Woman agrees to use acceptable contraceptive methods or alternative methods during the study as described below and, if applicable, upon study treatment discontinuation, as defined by the local prescribing information (see Section 4.6.1).

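### SAP 4.6.3 counts postpartum relapses from birth, so the early intervals can mix untreated and treated time; the one infusion-anchored count leaves out women starting ocrelizumab and those resuming after a long gap

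*SAP*

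**What the plan says.** SAP 4.6.3 (Women's Disease Activity) sets the main relapse summary for the Full Analysis Set of mothers (FASM): "Number of relapses before/during pregnancy (defined by LMP) and after pregnancy (defined as after birth) will be summarized in 3-month intervals". The number and percentage of women by relapse category use the same before, during and after pregnancy intervals. A further bullet allows an annualized relapse rate with 95% CI in 3-month intervals if the data warrant it. That bullet names no time origin.

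The same section has a second, narrower block, headed "Among women who received their last ocrelizumab within 12 months before the LMP". It pairs relapses 6 to 9 months after the last dose before baseline with relapses in the three months that follow the first postpartum dose. This is the only relapse count in the section that starts at the infusion.

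On timing, Protocol 3.1.3 states: "The first dose of ocrelizumab may be administered at any point between Week 2 and Week 24 postpartum". Protocol 4.1.1 sets the same limits through the infant's age: "Infant is between 2–24 weeks of age at the time of the mother's first postpartum dose of ocrelizumab".

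In Protocol Section 2 (Table 1) the objective is exploratory: disease activity in lactating women who receive ocrelizumab after delivery. Its relapse endpoint is the number of clinical relapses over the postpartum period, with no reference to the infusion date.

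**The concern.** A relapse between delivery and the first infusion is untreated disease activity. One after the infusion is activity under ocrelizumab. When both fall in the same row, the row describes neither, and its value depends partly on how late women happened to be infused. A woman infused at Week 13 or later contributes no treated time to the 0-3 month row.

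The section already has the right tool, a three-month count from the first postpartum dose, but limits it to one subset. Women starting ocrelizumab are a planned part of the population (SAP Section 2 describes the 2 × 300 mg regimen for them). They fall outside the subset, as do women resuming after more than 12 months. For them the first months after the dose are visible only through the mixed birth-anchored rows. What is at stake is whether an exploratory table can be read, not any confirmatory conclusion.

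**Working it through.** **Plan's own figures.** The documents give no calculation for relapses. Their only precision statement (SAP 2.2, 10 infants) reproduces with exact Clopper-Pearson limits: widths 0.4425 and 0.5309 for one and two events, and an upper limit of 0.3085 for none, against 0.443, 0.531 and 0.31. The last figure shows how little 10 women can say about relapse on either clock: 0 of 10 is compatible with a risk up to 0.31.

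**Inputs.**
- Time origin: birth, in 3-month intervals, taken as 13 weeks (SAP 4.6.3).
- Infusion time t: between 2 and 24 weeks after birth (Protocol 3.1.3, 4.1.1). The distribution within that range is not given, so several are tried as assumptions.

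**Pre-infusion share of months 0-3** = E[min(t, 13)] / 13.
- All at Week 2: 2/13 = 15%.
- Uniform over Weeks 2-6: mean t is 4, and 4/13 = 31%.
- Uniform over Weeks 2-24: E[min(t, 13)] = [(13² − 2²)/2 + 13 × 11]/22 = (82.5 + 143)/22 = 10.25, and 10.25/13 = 79%.
- All at Week 13 or later: 13/13 = 100%.

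**Pre-infusion share of months 3-6**, uniform over Weeks 2-24: E[max(t − 13, 0)]/13 = (11²/2)/22/13 = 2.75/13 = 21%. It is zero if all infusions fall before Week 13.

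**Month 6 onward.** Six months is about 26 weeks and the latest permitted infusion is at 24 weeks, so the pre-infusion share is zero for every woman.

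**What the mix could do to the count (illustration only).** Protocol 1.3 states: "About 30% of women experience a relapse in the first 3 months postpartum". Assume 10 women, that risk, a constant hazard, one relapse per relapsing woman and, as an extreme, complete suppression from the infusion. The expected 0-3 month count is 3.0 with no suppression and 3.0 × share with full suppression.

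| Infusion timing | No suppression | Full suppression |
|---|---|---|
| All at Week 2 | 3.0 | 0.46 |
| Uniform, Weeks 2-6 | 3.0 | 0.92 |
| Uniform, Weeks 2-24 | 3.0 | 2.4 |
| All at Week 13 or later | 3.0 | 3.0 |

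With Poisson counts, the chance of seeing at most one relapse is 0.20 at a mean of 3.0, 0.32 at 2.36 (Weeks 2-24, before rounding) and 0.77 at 0.92 (Weeks 2-6). How far the row reflects treated disease activity therefore depends on the infusion dates.

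**The case against.** The SAP implements the protocol. The endpoint is defined over the postpartum period, so counting from birth is faithful to it. The sibling EDSS endpoint ends at baseline, so the objective can be read as describing a population, not treated time. The remark in Protocol 3.3, "These endpoints are commonly used in MS clinical trials to assess treatment efficacy and disease progression", is general and declares no efficacy aim here. The study is single-arm and descriptive, with no confirmatory hypothesis. The 12-month restriction has a purpose, because it pairs the count after the last dose with the count after re-dosing. Relapses are listed, time from delivery to first infusion is summarized (SAP 4.3.1), and serious relapses enter the SAE tables from the first postpartum infusion for all mothers (SAP 4.8.2).

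Most of this stands, and it keeps the point minor. It does not remove it. A listing leaves the reader to build the summary. The SAE tables cover only serious relapses, over the whole study. The pairing justifies a subgroup row, but not leaving other women out of the post-dose count.

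Some stronger readings are tempting but not supported:
- A reader might infer that the first 3-month count would look almost the same whether ocrelizumab stopped all relapses or none. That holds only if infusions are mostly late. With Weeks 2-6 the illustration gives 3.0 against 0.92.
- A reader might infer that women outside the subset have no post-infusion relapse summary at all. Every birth-anchored interval from month 6 is post-infusion for everyone.
- A reader might infer that the annualized rate starts at birth. The SAP does not say.
- A reader might set 3.0 against 0 on an infusion clock. That carries the 30% figure, given for the first three months after delivery, to a window that can open at Week 24. Protocol 1.3 also reports lower relapse hazards with breastfeeding (0.57 pooled, 0.37 exclusive), so 30% may be too high for these women.
- A reader might suppose that pre-infusion relapses prompted treatment. Protocol 3.1.2 says such decisions are usually made before or during pregnancy.

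**Conclusion.** The point holds as a minor, cheap improvement to an exploratory endpoint. The 0-3 month row can mix pre- and post-infusion time, with a pre-infusion share from about 15% to 100% depending on dates the documents do not give. The 3-6 month row can mix them too, with 21% pre-infusion under uniform timing over Weeks 2-24. Later rows are clean. Women starting ocrelizumab, or resuming after more than 12 months, lack an infusion-anchored relapse count for the early post-dose period.

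The shares rest only on the stated window and the assumed timing. The relapse counts also rest on the 30% figure, a constant hazard and full suppression from infusion, and serve only to show sensitivity to timing. Nothing here supports saying that the table is uninformative or that the plan departs from the protocol. With about 10 women, any version of the count will be imprecise.

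**What to change.** In SAP 4.6.3:
1. Report the three-month count after the first postpartum dose for the whole FASM. Keep the 12-month restriction as a subgroup row, so that its paired comparison survives.
2. Split postpartum relapses and person-time at the date of infusion 1, giving both for each part.
3. State the time origin of any annualized relapse rate.
4. Keep the birth-anchored table as a description of the postpartum course, which preserves the protocol's wording.

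Relapses already go on a dedicated form (Protocol 4.5.2.5) and infusions are recorded, so no new data collection should be needed. The split needs a line on partial dates: the rule in SAP 4.3.1, which sets a missing day to the first of the month, would usually place a relapse in the infusion month before the infusion. The cost is SAP wording and one extra table with sparse counts.

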4.6.4 Infant Evolution of B Cell Levels

To evaluate the evolution of B cell levels over the first year of life, B cell levels (CD19+cell, absolute counts and percentage of lymphocytes) are collected in the infant at Day 30 Visit and 1 month after the first dose of MMR vaccine or at Month 13 of age if MMR vaccine is not planned to be administered.

Summary statistics for the mean absolute values and percentage change from Day 30 will be presented at each visit (Day 30, 1 month after first MMR vaccine, Month 13 of age if MMR vaccine is not administered) for absolute CD19+ cell counts and percentage of lymphocytes based on the FASI, irrespective of the occurrence of any ICEs identified for the primary endpoint.

The proportion of infants with CD19+ B cell levels below LLN, and summary statistics for the result, will be presented by visit (Day 30, Month 13).

Subject profile plots (one line per infant) will be used to display the trajectory of CD19+ cell levels (absolute counts and percentage of lymphocytes) over time in the FASI. The Y axis will be the absolute cell count or percentage of lymphocytes, and the X axis will be age in weeks. Lines will be plotted based on the actual age (i.e., not pooled into age categories). The age-specific LLN and ULN (see Appendix 3) for CD19+ cell counts and percentage of lymphocytes will be overlayed.

All B cell data collected will be listed. This listing will flag cases where absolute cell counts at each visit fall below the age-specific LLN for CD19+ (based on Borriello et al. 2022 [see Appendix 3]), and for CD3, CD4, CD9 and CD16+56 (based on Tosato et al. 2015 [see Appendix 4]).

4.6.5 Feeding Schedule / Feeding Status

The following Feeding Schedule Diary data will be presented by Study Day in the FASM (noting that Study Days 13, 14, 15, 16, 20, 21 and 22 should only be completed for subjects who receive 2×300 mg ocrelizumab infusions in 2 separate visits):

- Number and proportion with each type of feed (breastmilk, partial breastmilk/infant formula, other feeds such as baby food)
- Mean number of breastmilk feeds
- Mean number of formula milk feeds

Mean number of other feeds (baby food)

After the 60-day sample period, woman may switch to another DMT and continue to breastfeed, this will be summarized as follows in the FASM:

 Number and proportion with each type of feed (breastmilk, partial breastmilk/infant formula, other feeds such as baby food) at Months 2, 4, 6, 9, and 12, by whether or not they switched to another DMT, regardless of timing

A corresponding listing will be produced.

